- Participants with a score of 15 or more on the PHQ-9 or indicated self-harm on question 10 will receive a phone consultation from a clinical psychologist on the research team. This call will ensure that they are under care elsewhere or necessary resources and/or referrals can be provided.

Recruitment Strategy

Recruited will involve many strategies including a television broadcast, promoting the study via tinnitus support groups in Texas and the American Tinnitus Association (ATA), and contracting the company "TrialFacts" to boost recruitment. Further recruitment strategies will involve the use of social media (e.g., Facebook and Twitter). Flyers and posters will be distributed to local communities and put up in clinic waiting rooms. Professionals such as audiologists and otolaryngologists in the state of Texas will be notified about the study and provided with leaflets to distribute to suitable patients. Those interested will be directed to the study website (www.tacklingtinnitus.org) where they can read more about the study and register their interest in study participation. Following registration, they will be invited to complete the screening questionnaire. They will be informed of their right to withdraw without penalty at any stage of the process.

Sample Size, Power and Attrition

Sample size estimation will be calculated using G*Power version 3.1.6 (Faul et al., 2007) and based on achieving a 13-point clinically meaning change between baseline and post-intervention using the primary assessment measure, the TFI. Pilot data (Beukes et al., Submitted) indicated 26 participants per group with a 1:1 allocation to achieve 80% power to detect a between-group mean standardized difference effect size of d = 0.50 (a moderate effect size). As this will be fewer than the 58 participants suggested using data from previous RCTs of this intervention, (Beukes et al., 2018) we selected 58 per group. In addition, sample size will be inflated to account for missing data, estimated to be 20% from the US phase I trial data (Beukes et al., 2021b). The aim will be thus to recruit 146 participants with 73 in each arm (calculated as 58/0.8).

Randomization

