Online questionnaires will be used throughout the study. All the measures will be completed at baseline, T1 (post-intervention for experimental group), T2 (post-intervention for the control group and at two-month follow-up for the experimental group). To have a measure of the control group 2 months post intervention, participants completed further outcome measures at T3. For data analysis purposes the T3 results for the control group and those at T2 for the experimental group will be compared in order to assess the invention effect at same experimental time point for both groups (i.e., 2 months post intervention). To maximize retention, 3 electronic reminders will be sent to participants who had not completed questionnaires, on the 3 consecutive days after the release of the questionnaire. A further reminder will be sent out via email and text message. If questionnaires will be still not completed participants will be telephoned to encourage questionnaire completion. Participants will be also phoned after completing the intervention to discuss the progress they had made and share their questionnaire results.

Statistical Analysis Plan

Statistical analyses will be performed using the Statistical Package for Social Sciences (SPSS) version 26.0. All statistical tests will be 2- tailed with an alpha set to .05. To account for missing data from participants not completing the post-intervention or follow-up intervention analysis an imputation analysis will be undertaken. Missing data will be handled through multiple imputation using the *Markov Chain Monte Carlo* approach (Jakobsen et al.,

2017). For comparison, a complete case analysis will be also performed by analyzing only the completed questionnaire data without imputing missing data. As there will be substantial differences, statistical analysis using the imputed data are reported in the results section.

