The primary study outcome will be a change in TFI score between the groups at postintervention (T1). A difference in scores between T1–T2 for the experimental group will be used to assess the stability of intervention effects. According to recommendations for statistical analysis of internet interventions effect sizes, linear mixed effects models, and the reliable change index will be used to assess the primary and secondary outcomes (Hesser, 2015). Changes from baseline to post-intervention will be compared within and between groups using the pre-post-test effect size (Cohen's *d*) for all primary and secondary outcomes using the observed data. Effect sizes of d = 0.20 represent small effect sizes; those of d =0.50, medium effect sizes; and those equal or greater than d = 0.80, large effect sizes (Cohen, 1992).

A Linear Mixed Model (LMM), which provides unbiased results in the presence of missing data (using all available data), will be applied to analyze the intervention effect over time for each outcome measure. An unstructured-repeated effects and identify-random effects covariance structure provided the best model fit based on the Akaike's Information Criterion (AIC). Time will be treated as a repeated and fixed effect. Restricted maximum likelihood estimation will be applied. The Type III F test sums of squares from the LMM will be calculated. As a sensitivity analysis, baseline tinnitus severity will be initially added as a covariate, but as it had no significant effect on the results it will be removed from the model.

Another model will be run to test the differences during the course of the 8 weeks intervention for the weekly outcome measures. Post hoc time comparison will be carried out in the case of significant group differences to assess at which time points these differences occurred.

In addition to statistical significant, clinical significance will also reported. A 13 point difference is recommended by the original developers of the TFI (Meikle et al, 2012) to indicate a meaningful change in scores. To handle study variability, the reliable change index (RCI) (Jacobson & Truax, 1991) is recommended as a means of calculating clinical significance for the TFI as the primary outcome. This will be calculated using the mean pretest-posttest score difference, the pretreatment standard deviation (17.49), and a test-retest reliability coefficient of 0.78, and as reported in the validation study

Sample Characteristics

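### The plan's only power statement does not follow from its inputs: 26 per group gives about 42% power at d = 0.50, not 80%, and no effect size or power is given for the 58 per group chosen

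*Combined protocol and SAP*

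**What the plan says.** All the sample size reasoning is in the protocol section *Sample Size, Power and Attrition*. It names G*Power as the software and describes the calculation as "based on achieving a 13-point clinically meaning change between baseline and post-intervention" on the TFI. Pilot data are then said to have indicated "26 participants per group with a 1:1 allocation to achieve 80% power to detect a between-group mean standardized difference effect size", and the size is given as "effect size of d = 0.50 (a moderate effect size").

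The plan does not use 26. It continues: "As this will be fewer than the 58 participants suggested using data from previous RCTs of this intervention", and selects 58 per group. Allowing for 20% missing data, this becomes 73 per arm, 146 in total.

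The *Statistical Analysis Plan* section supplies the rest:
- Error rate: "All statistical tests will be 2- tailed with an alpha set to .05".
- Primary comparison: "The primary study outcome will be a change in TFI score between the groups at postintervention (T1").
- Model: a linear mixed model, in which "Time will be treated as a repeated and fixed effect". Baseline severity is tried as a covariate and then removed.
- A TFI SD and a test-retest coefficient (0.78) appear only as inputs to the reliable change index: "the pretreatment standard deviation (17.49").

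**The concern.** Once the number of groups, allocation ratio, alpha, power and standardised difference are all stated, the sample size for a simple two-group comparison is fixed. For 80% power at a moderate effect it is well known to be in the sixties per group, so 26 is conspicuous.

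Two further gaps add to this. The number actually used, 58, has no effect size, SD or power attached. The paragraph also cites both a 13-point change and a between-group d of 0.50, with no SD to connect them.

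What is at stake is how the result will be read. Setting 58 against 26 suggests a wide margin for a moderate effect. A reader facing a null or borderline result could then conclude that a moderate effect had been all but excluded, when the trial may not have had the power to support that.

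**Working it through.** **Inputs from the documents.** Two groups, 1:1; two-sided alpha .05; d = 0.50; 26 and 58 per group; 20% missing. SD 17.49 and coefficient 0.78 are given only for the reliable change index. All baseline-to-T1 correlations (r) below are assumptions.

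**Formula.** For a two-sample t test with n per group, the noncentrality is δ = d·√(n/2) on 2n − 2 degrees of freedom. Power is the probability that a noncentral t with that δ falls beyond the two-sided 5% critical value.

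**1. The plan's own figure.** n = 26: δ = 0.50·√13 = 1.80, df = 50, critical value 2.01. Power is **42.4%**, not 80%.

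**2. What the stated inputs require.** Solving for 80% power at d = 0.50 gives n = 63.8, so **64 per group** (80.1%). With 26 per group, 80% power is reached at d = 0.79. The size 26 is also what d = 0.80 would need (n = 25.5, rounded up).

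**3. The chosen size.** n = 58: δ = 0.50·√29 = 2.69, df = 114. Power is **76.1%**. 80% power is reached at **d = 0.525**.

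**4. Other readings of 26 per group at d = 0.50.**

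| Reading | Power | Difficulty |
|---|---|---|
| One-sided, two-sample | 55.3% | contradicts the two-tailed rule |
| 26 as total (13 per group) | 23.2% | contradicts the per-group wording |
| Two-sided paired test, n = 26 | 68.8% | not a between-group test |
| One-sided paired test, n = 26 | 79.8% | contradicts both |
| Change contrast, r = 0.78 | 76.0% | r not given for this purpose |
| Baseline-adjusted, r = 0.78 | 80.7% | r not given for this purpose; covariate is removed |

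With d in raw-score SD units, the change contrast uses d/√(2(1 − r)) and the baseline-adjusted comparison uses d/√(1 − r²). To reach 80% with 26 per group, the first needs r = 0.80 and the second r = 0.78. If d is already in change-score SD units, the change contrast is simply the two-sample result, 42.4%.

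**5. Sensitivity of the planned analysis to r** (d = 0.50 in raw-score SD units):

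| Assumed r | Change contrast, n = 26 | Change contrast, n = 58 | Baseline-adjusted, n = 58 |
|---|---|---|---|
| 0.3 | 32% | 62% | 80% |
| 0.5 | 42% | 76% | 87% |
| 0.6 | 51% | 85% | 92% |
| 0.78 | 76% | 98% | 99% |

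For the change contrast, 58 per group reaches 80% at r of about 0.55.

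**6. The 13 points.** If 13 points is read as a between-group difference:
- It equals d = 0.50 only if the SD is 13/0.50 = 26.
- 58 per group, unadjusted, has 80% power for it if the SD is at most 13/0.525 = 24.8.
- If the SD were 17.49, d would be 13/17.49 = 0.74. Power would be 98% with 58 per group and 75% with 26.

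**7. Inflation.** 58/0.8 = 72.5, rounded up to 73 per arm. This step reproduces.

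**The case against.** The strongest reply is that 26 comes from a pilot report outside the documents, and that the paragraph names neither the test nor the units of d. A high baseline-to-T1 correlation would reproduce it, as step 4 shows. So would G*Power's group-by-time routine with f = 0.25, two time points and an assumed r of 0.2. There λ = 0.25²·52·2/0.8 = 8.125, and power is 79.8% at 52 in total. On this view the figure is under-documented rather than false.

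Part of that stands. The documents cannot show whether an input was left out or the wrong d was written. But the sentence as printed states a between-group d of 0.50 and no correlation, and on those terms it is wrong. The group-by-time route does not rescue it. With δ = √8.125 = 2.85, the difference in change is 2.85/√13 = 0.79 change-score SDs. That is 0.79·√1.6 = 1.0 raw-score SD, twice the stated effect.

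Second, 26 was set aside for a larger number and drives nothing. That is true and limits the harm, but it does not remove it. This is the only power statement in the documents, and it is the yardstick against which 58 is made to look generous.

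Third, the unadjusted 76% may be too low or too high for the planned change-score or mixed-model analysis. This also stands: step 5 spans 62% to 98% for the change contrast. It is a reason to state the assumed correlation, and to label any figure given without one as unadjusted.

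Fourth, the plan calls 13 points a change from baseline and never equates it with d. That is fair. The figures in step 6 are conditional illustrations, and the main finding does not depend on them.

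**Conclusion.** The concern holds. For a two-sided, unadjusted comparison at alpha .05, 26 per group gives 42% power at d = 0.50. The stated 80% would need 64 per group, about 2.5 times as many (64/26). The readings that recover 26 either contradict the plan's wording, test a larger effect, or need a correlation of about 0.78 to 0.80 that the sample size section does not give.

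The chosen 58 per group has no stated effect size, SD or power. Unadjusted, it gives 76% at d = 0.50 and 80% at d = 0.525. Its power under the planned analysis cannot be worked out from the documents. It could be ample, for example 98% for a 13-point between-group difference if the SD were 17.49.

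This is a false justification that should be corrected. It is not evidence that the recruitment target is wrong.

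**What to change.** Rewrite the one paragraph:

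- Delete the claim that 26 per group gives 80% power at d = 0.50.
- State what 58 provides, for example: *With 58 evaluable participants per arm (73 randomised, allowing for 20% missing), a two-sided test at alpha .05 without baseline adjustment has 80% power for a between-group d of 0.525, and 76% for d = 0.50.*
- Give the effect size and SD from the earlier trials that led to 58.
- Use one basis: either a standardised difference, or 13 points with its SD and a clear statement of whether it is a within-group change or a between-group difference.
- If power is quoted for the change contrast, the mixed model or a baseline-adjusted analysis, state the assumed baseline-to-T1 correlation. For example, baseline adjustment at an assumed r of 0.5 gives 87% at d = 0.50 with 58 per group.

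The cost is one reworded paragraph and a less favourable stated power. Recruitment stays at 73 per arm, and the analysis does not change.

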Throughout the program, participants will be monitored weekly by means of the Tinnitus Handicap Inventory, Screening version (THI-S). The THI-S consists of a 10-item questionnaire and scores are comparable (r = .90) with the full version of the THI (Newman et al, 2008). The weekly scores will be also used to detect possible adverse effects. If scores increased by more than 10 points between two consecutive weeks, this will be noted as an adverse effect. Those indicating adverse effects will be contacted to address the identified problems. Participants will be also monitored by a newly developed Tinnitus Qualities Questionnaire (TQQ; Beukes et al., 2021a). The TQQ measures tinnitus qualities such as pitch, loudness, and the number of tones heard. The scores of TQQ can range between 0 to 100 with higher scores indicating more problematic tinnitus.

Intervention Variables

Intervention compliance will be assessed by determining retention rates and compliance in completing outcome questionnaires. Intervention engagement will be assessed by the number of logins, the number of modules read, and the number of messages sent during the intervention. Adverse effects will be monitored by 1) Direct questioning in the outcome questionnaire regarding the presence of adverse effects 2) Adverse effects written in messages or worksheets 3) An increase of 10 points or more during weekly monitoring using the THI-S questionnaire.

Questionnaire Administration

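### Adverse effects after a participant stops responding have no stated route of capture, and the planned call to non-responders is not said to ask about them

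*Combined protocol and SAP*

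**What the plan says.** Intervention Variables lists three ways of finding adverse effects. The first is "Direct questioning in the outcome questionnaire regarding the presence of adverse effects". The second is whatever the participant happens to report in free text, whether to the guide or in the program's exercises. The third is a THI-S score that goes up by at least 10 points in the weekly monitoring.

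Questionnaire Administration sets the mode ("Online questionnaires will be used throughout the study") and the schedule: baseline, T1 and T2 for both groups, and T3 for the control group only. Late responders get three electronic reminders, then one by email and text. After that, "If questionnaires will be still not completed participants will be telephoned to encourage questionnaire completion". A separate call after the intervention covers progress and questionnaire results. Neither call is listed as an adverse-effect source.

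The weekly monitoring section says that people who indicate an adverse effect will be contacted about it. Table 1 schedules the weekly measures only during the 8-week program.

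On attrition, Sample Size, Power and Attrition states: "sample size will be inflated to account for missing data, estimated to be 20% from the US phase I trial data". The Statistical Analysis Plan imputes data for participants who miss the post-intervention or follow-up assessment. It gives no analysis, denominator or missing-data rule for adverse effects.

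**The concern.** Non-response may be informative about harm. Someone whose tinnitus or distress worsens may stop submitting scores and ignore the questionnaire for that very reason. All three sources then fall silent together. The plan does arrange live contact with such people, but it does not say that they will be asked about harm.

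At stake is the adverse-effect rate of a largely self-directed online program. If those who leave because they worsened are under-represented, the observed rate is too low. With no stated denominator, a reader could not tell how many participants had been assessed. A participant who never indicates a problem is also outside the planned contact about adverse effects. The primary TFI analysis is not affected.

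**Working it through.** **Reproducing the plan's figure.** From Sample Size, Power and Attrition: 58 per group and 20% missing. 58 / 0.8 = 72.5, rounded up to 73 per arm, or 146 in total. This matches the plan.

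**How many would lack the direct question.** 0.20 × 146 = 29.2. Equivalently, 146 − 2 × 58 = 30. So about 29 to 30 people, taking the 20% as the share without the outcome questionnaire and the adverse-effect question as part of that questionnaire.

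**What each source needs, by period.**

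| Source | During the 8-week program | Two-month follow-up (T1–T2 experimental, T2–T3 control) |
|---|---|---|
| Direct question | Questionnaire at the end of the period | Questionnaire at the end of the period |
| Messages, worksheets | Participant must write | None scheduled; guidance is described for the intervention period |
| Weekly THI-S | Participant must submit; the weekly monitoring section judges the rise between two consecutive weeks | Not scheduled (Table 1) |

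During the program, the weekly THI-S can catch worsening before a person stops. It misses someone who worsens and skips the next score. In the follow-up, the outcome questionnaire is the only scheduled source.

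**How many would have no adverse-effect data at all.** Let *f* be the fraction of the 30 who gave no weekly score, message or worksheet. The documents do not give *f*.

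- *f* = 0: 0 people
- *f* = 0.25: 7.5 people (5% of 146)
- *f* = 0.5: 15 people (10%)
- *f* = 1: 30 people (21%)

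**Effect on the observed rate.** Let *k* = 30*f* be the number wholly unobserved, 5% the rate among the other 146 − *k*, and *p* the rate among the *k*. Both rates are assumptions.

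Overall rate = [0.05 × (146 − *k*) + *p* × *k*] / 146

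| *k* | *p* = 10% | *p* = 20% | *p* = 30% |
|---|---|---|---|
| 15 | (6.55 + 1.5)/146 = 5.5% | (6.55 + 3.0)/146 = 6.5% | (6.55 + 4.5)/146 = 7.6% |
| 30 | (5.8 + 3.0)/146 = 6.0% | (5.8 + 6.0)/146 = 8.1% | (5.8 + 9.0)/146 = 10.1% |

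The second term in each bracket is the expected number of unseen events: 1.5 to 4.5 if half of the 30 are wholly unobserved, and 3 to 9 if all are. If *k* = 0, or if *p* is also 5%, this calculation shows no bias.

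**The case against.** The strongest reply is that the plan already watches for harm before people leave. THI-S scores come in weekly, worsening will often precede stopping, and anyone flagged is contacted. The questionnaire is pursued through several reminders and a call, and a successful call leads to the very instrument that contains the adverse-effect question. A person can also abandon the modules and still answer it. All of this stands, and it limits the point to harm that emerges, or would have been reported, after responses cease.

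It also rules out some stronger readings that a reader might infer:

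- **That the 20% contribute no adverse-effect data.** The 20% is an allowance for missing outcome data, not a rate of total silence. Thirty wholly unobserved people is the upper bound.
- **That the adverse-effect rate would describe completers only.** Non-completers can contribute weekly scores and messages, and the analysis plan defines no adverse-effect rate.
- **That harm mentioned in a call would go unrecorded.** The documents do not say so. They only fail to say that it will be asked about.
- **That under-counting is worse in the ICBT arm.** This is plausible, since the program itself can be the reason for leaving, but the 20% is not split by arm and nothing else in the documents shows it.

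It may also be said that some wording in the Statistical Analysis Plan reads as if results were already known, so new call questions may come too late. The documents do not settle this. If it is so, the reporting half of the remedy still applies.

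**Conclusion.** The point holds in a limited form: every stated source relies on participant-submitted entries, and no staff-initiated enquiry about harm is described for someone who stops responding. About 29 to 30 of 146 would lack the direct question. The number with no adverse-effect data from any source lies between 0 and about 30, and the documents do not narrow it. The gap is clearest in the two-month follow-up.

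The direction of bias, an observed rate that is too low, depends on harm being more frequent among non-responders. Its size rests entirely on assumed rates, so the 6% to 10% range is the extreme case and should not be read as an estimate. Two simplifications matter. People who gave some data before stopping are treated as fully observed, although they were seen only up to that point. The 20% is also applied as one figure, although missingness may differ between T1, T2 and T3.

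This is a cheap improvement to harm ascertainment, not an error or contradiction in the plan.

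**What to change.** - In the existing call to non-responders, ask the questionnaire's own adverse-effect question. Ask those who have stopped the program for the main reason. Record the answers even if the questionnaire is never completed. This applies at T1 and T2 for both arms and at T3 for the control group only.
- List the call as a fourth adverse-effect source under Intervention Variables.
- In the Statistical Analysis Plan, report adverse effects by arm with the number actually assessed as denominator. Show online and telephone answers separately, and give the number with no assessment by any route.

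The cost is one or two questions in a call already planned, and a few lines in a table. No new visit, instrument or participant is needed. There are two drawbacks: the mode of collection becomes mixed, which is why the answers are shown separately, and some non-responders will not be reached, so the gap narrows but does not close. If data collection has already ended, only the reporting change is available. It would still show how many in each arm were assessed.
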